4.3.2. Records Retention

Data will be stored electronically for six years in the secure online platform RedCap and on the password-protected computer of the PI [name]. After three years the files will be permanently deleted.

5. HUMAN SUBJECTS PROTECTION (RISKS, BENEFITS, AND ALTERNATIVES)

5.1. Risks

This study poses minimal physical or psychological risk to the study participants. There is a risk that guardians will find the intervention time-consuming. If the burden of the intervention becomes too great, the participant can leave the study with no consequences.

Any adverse events related to the research study will be reported immediately to the IRB. Reportable events include any physical or psychological harm to any human that is related to the study intervention. Protocol deviations will also be reported to the IRB, including anything related to the study participants' safety, rights, or integrity of the study data.

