The x-IHPC will include 4 extra modules, (= 4 additional weeks of programming) that will be developed by a dietitian curriculum specialist. The expanded IHPC will also include programming just for parents to increase their involvement. A key pillar of this study is identifying and training CHWs from HWNV to be Spanish-language facilitators of x-IHPC. Training these CHWs and including them in designing the x-IHPC curriculum will ensure that the programming is culturally appropriate; includes local features that relate directly to the community's needs; and enables facilitators to respond effectively to the questions and learning needs of the parents and children involved in the program.

IHPC provides produce boxes, nutrition and meal-preparation, education, and supportive counseling to address barriers related to obtaining produce and food. The intervention provides participants with a bi-weekly produce box for 12 weeks (6 boxes total) and helps families identify sustainable ways to obtain vegetables once the produce boxes end. Providing produce boxes exposes families to new, unfamiliar vegetables that are not common in their home countries, and allows families to experiment with new recipes on a limited income. The CHW will support families by coaching them on how to prepare these unfamiliar vegetables, give tips on finding sales at grocery stores, as well as by navigation to food assistance sites including food pantries, school meal sites and bus routes, and neighborhood food distributions. Parents will learn strategies to increase vegetable consumption by addressing perceived

barriers – such as the child doesn't like vegetables. Curriculum will also include topics such as how to increase physical activity and reduce screen time. Both the families in the x-HPC and families who receive the in-office counseling will be offered the 6 vegetable food boxes, delivered on a bi-weekly basis during their time in the study.

Families will decide if they have the capacity to participate in the x-HPC intervention. They will be offered both groups, but can choose which group works for their family. We realize that this introduces selection bias into the study (families who self select to be part of the intervention are families who are interested in health and have the time and ability to attend). However, the intervention takes a lot of time and families need to choose the arm that works for their schedule.

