3.2. Comparison Group

A comparison group of similar families who receive standard nutrition, exercise, and weight-related lifestyle counseling during their regularly scheduled check-ups at HWNV will serve as the comparison group for this program. Both groups of children and guardians will receive standard in-office counseling, but the intervention group will also receive the x-IHPC intervention. Standard in-office counseling includes standard counseling related to diet, exercise, and screen behaviors,. The comparison group will also get food boxes.

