3.5. Consent/Accent

Once a guardian has been screened as eligible for inclusion in the study, they will be approached by the physician PI and asked if they are interested in being part of the study. If they are interested, the PI will discuss whether they are interested in joining the comparison group or the intervention group. A member of the study team will meet with the family virtually or in person and consent the guardian to be part of the study (Appendix D: Consent). This consent process will take place with a trained interpreter. The consent will be provided in both English and Spanish. The consent will be emailed to program participants prior to the

¹⁵ Bryant, M. J., Ward, D. S., Hales, D., Vaughn, A., Tabak, R. G., & Stevens, J. (2008). Reliability and validity of the Healthy Home Survey: a tool to measure factors within homes hypothesized to relate to overweight in children. *The international journal of behavioral nutrition and physical activity*, 5, 23. <https://doi.org/10.1186/1479-5868-5-23>

¹⁶ Schrempf, S., van Jaarsveld, C. H., Fisher, A., & Wardle, J. (2015). The Obesogenic Quality of the Home Environment: Associations with Diet, Physical Activity, TV Viewing, and BMI in Preschool Children. *PloS one*, 10(8), e0134490. <https://doi.org/10.1371/journal.pone.0134490>

¹⁷ Kininmonth, A. R., Schrempf, S., Smith, A., Dye, L., Lawton, C., Fisher, A., Llewellyn, C., & Fildes, A. (2021). The Home Environment Interview and associations with energy balance behaviours and body weight in school-aged children - a feasibility, reliability, and validity study. *The international journal of behavioral nutrition and physical activity*, 18(1), 167. <https://doi.org/10.1186/s12966-021-01235-3>

consent conversation when possible. Whether consent occurs virtually or in person, a hard copy of the consent will be printed and stored by the Inova PI. A copy of the consent will be given to the guardian.

3.6. Monitoring Subjects and Criteria for Withdrawal of Subjects from the Study.

Study participants may leave the study at any time, without penalty. In some cases, the participant may be withdrawn if the HWNV physician PI determines that the study intervention is too burdensome for the participant or is adversely affecting the study participant's health. If any study participant leaves the study or is withdrawn from the study, their data will not be used in analysis.

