4.2. Method of Data Analysis

Analyses will follow the intention-to-treat principle, which categorizes participants by their treatment assignments regardless of adherence to the intervention or incomplete follow-up, and includes them in all analyses. Descriptive statistics will be calculated and reported as mean, standard deviation and 95% confidence intervals for continuous variables and frequency and percentage for categorical variables. Characteristics of study participants will be compared at baseline between the intervention and control groups and tested for significance using the two-sample t-test for continuous variables and the Chi-square test for categorical variables. Comparisons that are significant at the $P<0.10$ level will be considered for inclusion in multivariable models for primary and secondary analyses given that participants will not be randomized to their respective treatment groups.

Primary analyses will examine diet quality, screen time, physical activity, and guardian self-efficacy and confidence of those in the intervention and control groups while controlling for the correlated nature of the repeated measures within participants (i.e. baseline, post-intervention, and 6-month post-intervention). Secondary analyses will compare the BMI of guardians and BMI percentile of children at the three time points between the intervention and control groups. A longitudinal data analysis strategy will be employed with generalized estimating equations with robust CIs for both primary and secondary outcomes (Albert, 1999; Ma et al., 2012). A 2-sided p-value <0.05 will be accepted to indicate statistical significance. Additional analyses will be conducted to determine if results were influenced by other covariates including demographics (age, gender, educational attainment of guardian, income, etc.). All analyses will be conducted in SAS version 9.2.

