5.2. Benefits

The benefits to participating in this study include improved knowledge about modifiable lifestyle behaviors that effect healthy eating and weight. A second benefit to participating in the study is that families will receive complimentary vegetable food boxes (6 boxes, delivered every other week) for the duration of their time in the study.

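### For families overburdened by x-IHPC, the protocol names only leaving or withdrawal from the study and then drops their data, which contradicts the intention-to-treat rule in 4.2

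*Combined protocol and SAP*

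**What the plan says.** Section 5.1 names the foreseeable problem, "There is a risk that guardians will find the intervention time-consuming", and gives the response: "If the burden of the intervention becomes too great, the participant can leave the study with no consequences".

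Section 3.6 gives the investigator's counterpart: in some cases "the participant may be withdrawn if the HWNV physician PI determines that the study intervention is too burdensome for the participant". It then sets the data rule: "If any study participant leaves the study or is withdrawn from the study, their data will not be used in analysis".

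Section 4.2 commits to intention to treat. Participants are analysed in their group "regardless of adherence to the intervention or incomplete follow-up, and includes them in all analyses".

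On where the burden comes from, section 3.1 (like 2.6) says: "However, the intervention takes a lot of time and families need to choose the arm that works for their schedule". Section 3.2 says what separates the arms: "Both groups of children and guardians will receive standard in-office counseling, but the intervention group will also receive the x-IHPC intervention". Both arms are offered the produce boxes.

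On how outcomes are collected, section 3.4 has the primary survey done by phone at the start and end of the study, and BMI taken at clinic visits. Neither requires attendance at a class.

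**The concern.** Two different events are treated as one. A family may find the classes too much and stop attending, or it may no longer wish to give data. For the first event, the text names only responses that belong to the second: leave, or be withdrawn. Once either happens, 3.6 removes the family from the analysis, including whatever it has already provided.

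The classes exist in one arm, so loss for this reason is unbalanced. It is also unlikely to be unrelated to outcome, because families who cannot keep up with the sessions are probably those who engage and change least. The x-IHPC families who remain would be a selected group, and the comparison would lean towards the intervention.

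Much of this loss is avoidable, because the closing call and the clinic measurement can be made whether or not the family attends sessions. The analysis rule and the conduct rule both matter. Deleting the exclusion sentence would bring back baseline values and any BMI already taken. It would not supply a closing survey from a family that was never asked for one.

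**Working it through.** **Passages side by side.**

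| Event | 5.1 and 3.6 | 4.2 |
|---|---|---|
| Family misses or stops classes but does not leave | Not addressed | Stays in the analysis |
| Family leaves because of burden | Permitted (5.1); data unused (3.6) | Incomplete follow-up, so included |
| Physician PI withdraws family because of burden | Permitted; data unused (3.6) | Incomplete follow-up, so included |

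The second and third rows are direct contradictions. The first row is a gap: 4.2 implies that such a family stays, but neither 3.6 nor 5.1 tells staff or families so.

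**Size.** The documents give 25 families per arm and a two-sided 0.05 level. They give no dropout rate, SD or effect size, and no planned figure to reproduce. Everything below is an assumption for illustration.

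Let p be the share of x-IHPC families lost for burden, S the mean change in those who stay and T the mean change that those lost would have shown, in SD units. Assume no loss in the comparison arm.

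- Mean change in all x-IHPC families: (1 - p)S + pT
- Mean change in those analysed: S
- Overstatement: S - [(1 - p)S + pT] = p(S - T)

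| p (of 25 families) | S - T = 0.3 | 0.5 | 0.8 |
|---|---|---|---|
| 10% (2.5) | 0.03 | 0.05 | 0.08 |
| 20% (5) | 0.06 | 0.10 | 0.16 |
| 30% (7.5) | 0.09 | 0.15 | 0.24 |
| 40% (10) | 0.12 | 0.20 | 0.32 |

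If S = T, the overstatement is zero at every p. If the comparison arm also loses a share p_c with gap g_c, the net figure is p(S - T) - p_c × g_c, so loss there of the same kind would offset it.

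**Cross-check with a selection model.** Suppose the families lowest on a latent capacity trait leave, and the trait has correlation rho with the outcome. The mean of those retained shifts by rho × φ(z_p)/(1 - p), where z_p is the normal quantile at p.

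| p | Shift, rho = 0.3 | Type I error | Shift, rho = 0.5 | Type I error |
|---|---|---|---|---|
| 10% | 0.06 | 5.5% | 0.10 | 6.4% |
| 20% | 0.11 | 6.4% | 0.18 | 9.2% |
| 30% | 0.15 | 7.7% | 0.25 | 13.2% |
| 40% | 0.19 | 9.2% | 0.32 | 17.8% |

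The type I error is for a single outcome under a two-sided 0.05 normal test with no true effect. At rho = 0 there is no shift. Dividing the shift by p gives the implied gap between stayers and stoppers: about 0.5-0.6 SD at rho = 0.3 (0.193/0.40 to 0.058/0.10) and about 0.8-1.0 SD at rho = 0.5 (0.322/0.40 to 0.097/0.10). The rho = 0.5 columns are therefore at or beyond the top of the range in the first table.

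**The case against.** Several stronger readings are tempting, and the documents do not support them.

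- **That a burdened family can only leave.** Both provisions are permissive, no attendance minimum is set, and 4.2 keeps non-adherent participants. A family that stops attending without leaving could remain. What holds is that leaving and withdrawal are the only routes named. The consent form (Appendix D) and the flow chart (Appendix A) are not in the text available, and either might say more.
- **That outcome collection stops at exit.** No sentence says so. The stated rule is that the data are not used, which is wider in one respect because it also discards data already in hand.
- **That the loss can arise in one arm only.** This is true of class burden. Section 2.5.4, however, uses the term study intervention to include surveys and counseling, so the 3.6 rule could reach a comparison family, and anyone may leave at any time. Mainly in the intervention arm is as far as the text goes.
- **That leaving carries a penalty because the produce boxes end.** Sections 5.1 and 5.3 read naturally as promising no sanction for leaving. The end of a benefit supplied by the study is not a contradiction.
- **That retaining stoppers would raise power.** If stoppers change less, keeping them dilutes the effect: with a stayer effect of 0.5 SD, p = 20% and a gap of 0.5 SD, it becomes 0.5 - 0.20 × 0.5 = 0.40 SD. The case for the change is bias, not power.

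Two further points stand. Families choose their arm by capacity, which may keep burden exits few. That self-selection is also a separate bias, acknowledged in 2.6 and 3.1, which no change here removes.

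**Conclusion.** The point holds in a limited form. Sections 3.6 and 4.2 contradict each other on the data of families who leave or are withdrawn. For class burden, 3.6 and 5.1 name only exits that trigger the exclusion. Followed as written, the plan would lose families mainly from the intervention arm, probably the less engaged ones, although their outcomes could still be requested.

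The overstatement is 0.03-0.32 SD, with 0.10 SD as a middle case. It rests on assumed loss of 10-40% in the x-IHPC arm, an assumed gap of 0.3-0.8 SD, and no loss in the comparison arm. It is zero if those lost do not differ from those who stay. The intention-to-treat comparison is not impossible, since only leavers are affected and their number is unknown. But each family is 4% of an arm (1/25), and the correction is cheap, so it should be made.

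**What to change.** 1. In 3.6 and 5.1, state that stopping x-IHPC sessions does not by itself end study participation. The family stays in its original group and is still asked for the closing phone survey and the scheduled office BMI, unless it declines further data collection or is withdrawn from the study.
2. Reconcile the 3.6 exclusion sentence with 4.2, so that data already collected, and any later data the family agrees to give, are analysed in the original group.
3. Record the date and reason for stopping sessions separately from the date and reason for leaving the study, in both arms where applicable.
4. Leave the participant's right to leave and the physician PI's authority to withdraw exactly as they are. Check that the consent form agrees with the revised text.

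The cost is a few sentences, any matching consent wording, and at most one extra call per stopper. The clinic visits already exist. Some families will decline the call, so the bias is reduced, not removed.

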5.2. Benefits

The benefits to participating in this study include improved knowledge about modifiable lifestyle behaviors that effect healthy eating and weight. A second benefit to participating in the study is that families will receive complimentary vegetable food boxes (6 boxes, delivered every other week) for the duration of their time in the study.

5.3. Alternatives

The alternative to participating in this research study is not to participate in the research study. There is no penalty to the eligible participants if they refuse to be part of the study or leave the study at any time.

5.4. Confidentiality

Every effort will take place to maintain the confidentiality of the study participants. Participants will be known to the physician study PI who is providing care during in-office clinic visits. Beside the PI and the co-PI at HWNV, no other HWNV staff member will have knowledge that the participant is part of the study. The PI and co-PI at HWNV will have an electronic list of participants who are part of the study, so they can provide the standard in-office counseling and data collection. The list will be accessed only by them on a password-protected document that is stored on password-protected computers at HWNV.

Survey data collected during the study will be uploaded directly into a secured online platform, RedCap, by the CHW collecting the data. Only the Inova and the HWNV PIs, will have access to this platform to manage data. Data will be de-identified before it is shared with the statistician for analysis. De-identification will occur by giving each participant a unique study ID. The document with participant names and unique study IDs will be kept on a password protected document on the Inova PI's password-protected computer.

6. SUBJECT COMPENSATION

6.1. Costs

There are no costs to being part of this study except for the usual and expected costs of attending a routine clinic visit.

6.2. Payment

There is no payment for taking part in this study. However, families will receive complimentary vegetable food boxes (6 boxes, delivered every other week) for the duration of their time in the study.

7. ADVERSE EVENT REPORTING

There is very low risk of adverse events in this study. Any adverse events (such as an abnormal physical exam finding that may be temporally related to the participant's involvement in the research) will be reported to the IRB immediately. Any unusual symptoms, actions, behaviors, or safety related events that occur during the study intervention activities will be reported immediately to the IRB. Any protocol deviations will be reported to the IRB immediately.

8. FUNDING

This study is supported in part by the National Center for Advancing Translational Sciences of the National Institutes of Health under Award Number UL1TR003015.

9. CONFLICTS OF INTEREST

There are no conflicts of interest from the PI or Co-PIs.

10. FACILITIES AND EQUIPMENT

In-office counseling will take place at the HWNV clinic building. The clinical building also supplies the computer equipment for the HWNV PI. The virtual platform (Zoom) and computer equipment for the x-IHPC comes from the Office of Community Engagement from the Inova health system. Storage for the boxes of x-IHPC supplies is also provided through this office. The office space and computer for PI [name] is provided through Inova Health System.

11. OUTSIDE CONSULTANTS/COLLABORATORS

The study statistician performing the data analysis is a consultant on this study. The statistician has a contract with the Inova Health System to provide statistical services.

Appendix A: Study Flow Chart

Do you want your kids to eat more veggies?

Healthworks & Inova invite you to Participate in a Research Study!

This Free Program Includes....

- **Virtual family cooking classes** or education during your clinic visits
- **Free Fruit & Veggie boxes** delivered to your home every other week
- Education about healthy kids & families

Interested?

If you are a patient at HealthWorks with a child between 6-12 years, and you speak Spanish at home, please ask your doctor about this program, or scan the QR code below to get more information!

Appendix C: Study Survey

Script and procedures for administration of the Buen Provecho! Study Survey

Adapted with permission from: Bryant, M. J., Ward, D. S., Hales, D., Vaughn, A., Tabak, R. G., & Stevens, J. (2008). Reliability and validity of the Healthy Home Survey: a tool to measure factors within homes hypothesized to relate to overweight in children. *The international journal of behavioral nutrition and physical activity*, 5, 23. <https://doi.org/10.1186/1479-5868-5-23>

The script

Administered By:

Date:

Start Time:

CALL PARTICIPANT

Good morning/evening. This is <your name>from <institute name>. Could I please speak to <participant name>?

Hello <participant name>. We have received the form that you mailed to us with consent to take part in our family home study. As we described in the consent form, the first part of the study involves a telephone interview which should take approximately 15 minutes. Is now a good time to conduct that interview with you?

If no *No problem. I will try again using another time that you suggested might be alright on your availability form. Thank you. Goodbye.*

If yes..... *Okay. I'll begin with a few general questions and then move on to more specific questions about your family home environment. Please feel free to stop me at any point or ask me to clarify any questions that you don't understand. There are no right or wrong answers. Please answer honestly. You are not being judged on any of your responses.*

What is your name?

* must provide value

What is your gender?

What is your ethnicity?

Hispanic or Latino - a person of Cuban, Mexican, Puerto Rican, South or Central American, or other Spanish culture or origin, regardless of race.
 Not Hispanic or Latino

What is your race?

American Indian
 Asian
 Hawaiian
 Black or African American
 White
 More than one race

What is your child's name?

* must provide value

What is your child's age?

* must provide value

What is your child's gender?

* must provide value

Are you the primary caregiver for < child's name> that you indicated as being suitable for this study?

* must provide value

Yes
 No

reset

What is your relationship with < child's name>?

How many adults older than 17 years live in your home?

* must provide value

Only include people who live in your home all of the time.

How many children under the age of 18 years live in your home?

Only include people who live in your home all of the time.

Are there parks, walking trails or outdoor recreation areas within safe walking of your home?

Is it safe for your child to play outside where you live currently?

How often does your child play outside - alone or with other children?

Do you or anyone else in your home have any medical conditions that impact your diet or physical activities behaviors?

Please think of right now, today:

Do you have any fresh fruit in your home?

Please think of right now, today:	
Do you have any fresh fruit in your home?	
Do you have any fresh vegetables in your home now?	
Where do you get most of your fresh vegetables?	
How do you use your fresh vegetables?	
Expand	
Do you have any ready to eat fresh vegetables on a shelf in the refrigerator or on the kitchen counter now?	
	
These include baby carrots, cherry tomatoes, or vegetables that you have sliced to make them ready to eat.	
Do you have any canned or jarred vegetables in your home?	
For canned vegetables: Where do you get them?	
How do you use your canned vegetables?	
Expand	
Do you have any frozen vegetables in your home?	
	
Can you tell me what frozen vegetables you have in your home?	
How do you use your frozen vegetables?	
Expand	
ok to say "I don't use them"	
Over the past 7 days, how often did your child eat vegetables?	
	
Do you feel that you have enough money in your budget each week to buy fresh fruits or fresh vegetables?	
	
Would it be possible for your child to get any salty snacks on their own, without your help?	
 Yes  No	
reset	
If we visited your home today, how many different salty snacks do you have in your home?	
(examples: chips, nuts, crackers)	
	

Do you feel that you have enough money in your budget each week to buy fresh fruits or fresh vegetables?	
Would it be possible for your child to get any salty snacks on their own, without your help?	 Yes  No
If we visited your home today, how many different salty snacks do you have in your home? (examples: chips, nuts, crackers)	
Would it be possible for your child to and get sweet snacks on their own, without your help?	 Yes  No
If we visited your home today, how many different sweet snacks do you have in your home?	
Would it be possible for your child to get soda on their own, without your help?	 Yes  No
Over the last month, how often did you eat lettuce salad (with or without other vegetables)?	
Each time you ate lettuce salad, how much did you usually eat?	
Over the last month, how often did you eat French fries or fried potatoes?	
Each time you ate French fries or fried potatoes, how much did you usually eat?	
Over the last month, how often did you eat other white potatoes?	
Count baked, boiled, and mashed potatoes, potato salad, and white potatoes that were not fried.	
Each time you ate these potatoes, how much did you usually eat?	
Over the last month, how often did you eat cooked dried beans?	
Count baked beans, bean soup, refried beans, pork and beans and other bean dishes.	
Each time you ate these beans, how much did you usually eat?	
Think about all the foods you ate at your morning meal and morning snacks this past week. On how many days did you eat vegetables for your morning meal or morning snacks?	
When your child ate vegetables with breakfast, what is the total amount of vegetables they usually ate?	

When your child ate vegetables with breakfast, what is the total amount of vegetables they usually ate?	
Think about all the foods you ate at your lunch meal and lunch snacks in the past week. On how many days did you eat vegetables for your lunch meal?	
When your child ate vegetables with lunch, what is the total amount of vegetables they usually ate?	
Think about all the foods you ate at your dinner/supper meal and snacks in the past week. On how many days did you eat vegetables for your dinner meal?	
When your child ate vegetables with dinner, what is the total amount of vegetables they usually ate?	
Think about all the foods your child ate for snacks in the past week. How often did they eat vegetables as snacks?	
When your child ate vegetables as snacks, what is the total amount of vegetables they usually ate?	
Over the last month, how often did you eat mixtures that included vegetables?	
Count such foods as sandwiches, casseroles, stews, stir-fry, omelets, and tacos.	
Over the last month, how often did your child eat tomato sauce? Include tomato sauce on pasta or macaroni, rice, pizza and other dishes.	
Over the last week, how often did your child eat tomato sauce?	
(Include tomato sauce on pasta or macaroni, rice, pizza and other dishes)	
Over the last week, how often did you eat vegetable soups?	
Include tomato soup, gazpacho, chicken soup with vegetables	
When your child ate vegetable soup, how much did they usually eat?	
Where do you eat dinner?	 In the same place every night (example - a dining room or kitchen)  A different place most nights  Almost every week night  2-4 times per week  0-1 times per week nights
I eat dinner with my children....	

Do you have the following at home?	 Microwave  Blender  Measuring cups AND spoons  A pot  Frying Pan
How do you usually heat your food?	 Oven / Stove  Microwave  Hot Plate  I do not have a place to heat food  Other
Would you say that you have adequate space to prepare food in your kitchen?	 Yes  No 
reset

Do you share a cooking space with individuals who are not in your family?	 Yes  No 
reset

Do you and your children eat dinner together (all in one room at the same time) or apart (different rooms or different times)?	
What do you drink with your dinner?	
Is there anyone else who is responsible for feeding your children? (example: aunt, brother, sister, grandparent, or "other" family if parents live separately)	
If "yes", then who is responsible for feeding your child?	
What does your child drink with dinner?	 Nothing, they don't drink during meals  Water  Juice  Soda  Milk
How many days a week does < child's name> eat breakfast?	
How many days a week does < child's name> eat breakfast at home?	
How many days a week do your family sit at a table to eat dinner together? This includes occasions when it is just < child's name> and yourself.	
How often does < child's name> eat breakfast in front of the TV each week?	
How often does < child's name> eat lunch in front of the TV each week?	
How often does < child's name> eat dinner in front of the TV each week?	
How often does < child's name> eat snacks in front of the TV each week?	

How often does < child's name> eat snacks in front of the TV each week?	
How often does < child's name> eat dinner away from home each week?	
How often does < child's name> eat fast food each week (example: McDonalds, Chik Fil A, taco bell, etc)	
Do you ask < child's name> to eat everything on their plate at dinner;	
Does your child have to eat all of their vegetables OR all of their dinner to get dessert?	
Do you reward < child's name> with desserts, snacks or candy if they finish foods from their plate at dinner:	
Do you allow < child's name> to have seconds if they finish foods from their plate at dinner;	
Do you allow < child's name> to serve themselves at dinner:	
Would you say that you serve the "same amount", "more" or "less" dinner to < child's name> compared to what you serve yourself?	
Do you allow < child's name> to help themselves to snacks, including salty and sweet snacks, or candy when they are at home:	
Does < child's name> help you shop for groceries at the store? For example, you may get them to pick their own foods, or give them their own grocery list.	
How many working TV's do you have in your home?	
On an average school day, how many hours does your child watch TV?	
How many tablets or ipads do you have in your home?	
How many working computers or laptops do you have in your home?	
How many working games consoles, such as Play Station or X-Box, do you have in your home?	
On an average school day, how many hours does your child play video or computer games or use a computer for something that is not school work? (Include activities such as Xbox, PlayStation, phone, tablet Nintendo DS, iPod touch, Facebook, and the Internet.)	

Does your child have their own phone (not one they borrow from a parent)?	 Yes  No
How often would you say that you restrict the amount of time < child's name> spends using a computer or laptop?	
From the following options, how often would you say that you reward good behavior with extra screen time?	
During the past month, other than your regular job, did you participate in any physical activities or exercises such as running, gardening or walking for exercise?	 Yes  No
How often would you say that you are active in the presence of your child?	
During the past 7 days, on how many days were you physically active for a total of at least 60 minutes per day? (Add up all the time your child spent in any kind of physical activity that increased their heart rate and made them breathe hard some of the time.)	
During the past 7 days, how many times did your child do a physical activity?	
How much time does < child> usually spend doing physical activities on one of those days? (can be hours or minutes)	
During the last 7 days, on how many days did < child> do moderate physical activities like carrying light loads, bicycling, playing on the playground, or playing basketball? Do not include walking.	
During the last 7 days, on how many days did < child> walk for at least 10 minutes at a time?	
How much water does your child drink each day?	
Do you feel that you need to change the amount of fruits and vegetables your child eats each week?	
How confident do you feel that you can increase the number of vegetables your child eats each week?	
How confident do you feel that you can obtain fresh fruit and vegetables for your family to eat during the week?	
How confident do you feel that you can cook healthy meals for your family?	
Do you feel that you need to change the amount of time your child spends using screens?	
